## **12.0 Data Safety Monitoring Board**

The Indiana University Adult Psychiatry Data Safety Monitoring Board (DSMB) will be responsible for data and safety monitoring. The DSMB is responsible for reviewing study procedures, adverse events, safety mailings (if applicable), enrollment, active subjects, and ongoing conduct of the research. The DSMB members can ask questions and make comments and/or recommendations. The IRB is notified of significant findings by way of the DSMB meeting minutes at the time of continuing review. Due to the small sample size and single site design of this protocol, there is not sufficient justification for conducting interim analyses to examine trends. Data on the number of subjects enrolled and the number of adverse events will be reviewed by the DSMB every six months and more frequently if needed. The resultant report will be issued to the Indiana University IRB at least at the time of continuing review or more frequently by request. Any unanticipated events will be immediately directed to the PI who will follow the Indiana University IRB reporting procedures.

## **13.0 Statistical Considerations**

### **Analyses**

#### *Power Analyses*

In terms of the power to detect a significant effect of precuneus directed rTMS on EM performance or neurocircuitry, there are no known calculations with EPP patients. We plan to enroll 30 subjects and anticipate a 20% drop out rate, thus yielding 24 completers. This is consistent with our previous clinical trial efforts in early phase psychosis populations, including a study of adjunct rTMS for cognitive impairment and negative symptoms. For all planned analyses, a total of 24 subjects in a cross-over design will result in 0.8 power to detect an assumed treatment difference at medium effect size 0.6; using an alpha level of 0.05 and conservatively assumed a within-subject correlation of 0.5. As no previous precuneus rTMS pilot study was available, this standardized effect size of 0.6 is considered to a conservative estimate to detect the significant results.

[figure not shown]

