## 2.0 Specific Aims and Hypothesis

The **first primary aim** is to demonstrate how targeting the precuneus with rTMS impacts functional activation (FA) in individuals with schizophrenia during EM tasks. We predict that, compared to sham stimulation, 1 Hz rTMS will result in decreased FA of the precuneus and 20 Hz rTMS will result in increased FA of the precuneus. The **second primary aim** is to demonstrate how targeting the precuneus with rTMS impacts precuneus functional connectivity (FC) in individuals with schizophrenia. We predict that compared to sham stimulation, FC between the precuneus, the DLPFC, the hippocampus, and the ACC will be decreased in response to 1 Hz rTMS and increased in response to 20 Hz rTMS. The **third primary aim** is to characterize the relationships between EM performance and changes in precuneus functional activation and connectivity. We predict that improved EM performance will be associated with increased precuneus functional activation and connectivity, while poorer EM performance will be associated with decreased precuneus functional activation and connectivity. The **secondary aim** is to characterize how targeting the precuneus with rTMS affects episodic memory performance in individuals with schizophrenia. We predict that compared to sham stimulation, 1 Hz rTMS will impair EM performance and that 20 Hz rTMS will improve EM performance.

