### *Sample Size*

We plan to enroll 30 subjects and anticipate a 20% drop out rate, yielding 24 completers. This is consistent with our previous clinical trial efforts, including a study of adjunct rTMS for cognitive impairment. For all planned analyses, a total of 24 subjects in a cross-over design will result in 0.8 power to detect an assumed treatment difference at medium effect size 0.6; using an alpha level of 0.05 and conservatively assumed a within-subject correlation of 0.5. As no precuneus rTMS pilot data was available, this standardized effect size of 0.6 is considered a conservative estimate to detect significant results.

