#### *Statistical Analyses*

[figure not shown]
Intent-to-treat (ITT) analysis will be conducted, and thus all randomized subjects will be included. ITT is the most conservative approach for detecting a treatment effect, because the inclusion of subjects who do not complete the intervention will serve to underestimate rather than overestimate any treatment effect. Sensitivity analyses including a subset analysis using a “completers only” analysis will be performed to test the robustness of the findings. Statistical tests will be performed based on two-sided test at the 5% level of significance.

Descriptive characteristics at baseline will be summarized for the whole sample. For continuous variables, the mean and standard deviation will be presented. For categorical variables, the number and percent will be reported.

Primary analyses: For each subject, change scores in activation of the precuneus (aim 1), functional connectivity (aim 2), and EM performance (aim 3) will be calculated at each treatment by using (post - baseline). We will employ a mixed model for repeated measures ANCOVA, of the general form for each measure:  $change_{ijk} = \mu + \alpha_i + b_{ij} + \gamma_k + \beta X_{ijk} + \tau_d(i, k) + e_{ijk}$ , where  $\mu$  is overall mean;  $\alpha_i$  is the effect of the  $i$ th treatment sequence ( $i = 1, 2, \dots, 6$ );  $b_{ij}$  is the random effect with variance  $\sigma_b^2$  for the  $j$ th subject ( $j = 1, 2, \dots, 24$ ) of the  $i$ th treatment sequence;  $\gamma_k$  is the period effect ( $k = 1, 2, 3$ );  $\beta X$  is the baseline value;  $\tau_d(i, k)$  is the direct effect of the treatment administered in period  $k$  of sequence group  $i$ ; and  $e_{ijk}$  is the random error with variance  $\sigma^2$  for the subject in period  $k$ . Based on this model, we will compare the treatment difference in change score between 1 Hz and Sham as well as 20 Hz and Sham. Under the assumption of missing at random, this mixed effect model will provide the unbiased estimates.

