Secondary analyses: We expect two mediation relations: (1) the treatment affects the connectivity through the activation of the precuneus; and (2) the treatment affects the EM performance through the activation of the precuneus. We use the first mediation as an example. The following 3 equations proposed by Baron and Kenny will be analyzed in order to establish mediation:  $change_{ijk} = \mu + \alpha_i + b_{ij} + \gamma_k + \beta X_{ijk} + \tau_d(i, k) + e_{ijk}$  (1);  $change_{ijk} = \mu + \alpha_i + b_{ij} + \gamma_k + \beta X_{ijk} + \gamma M_{ijk} + \tau_d(i, k) + e_{ijk}$  (2); and  $M_{ijk} = \mu + \alpha_i + b_{ij} + \gamma_k + \beta X_{ijk} + \tau_d(i, k) + e_{ijk}$  (3). Four steps are to be evaluated. First, a significant relation of treatment to the change in connectivity is required in (1). Second, a significant relation of treatment to the change in activation of the precuneus is required in (3). Third, mediator, the change in the activation of the precuneus, must be significantly associated with change in connectivity when both treatment and mediator are controlled as covariates. Fourth, the coefficients of treatment in (1) must be larger (in absolute value) than the coefficients of treatments in (2). If four steps are met, we will consider that the change in activation of the precuneus is mediator of the relationship between treatment and change in connectivity.

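### The stated 0.8 power is right for each active-versus-sham contrast but does not carry over to the four-step mediation rule, and having no pilot data does not make 0.6 conservative (minor wording correction)

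*Combined protocol and SAP*

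**What the plan says.** The power statement appears in section 3.0 (Sample Size) and again, nearly word for word, in section 13.0 (Power Analyses): "For all planned analyses, a total of 24 subjects in a cross-over design will result in 0.8 power to detect an assumed treatment difference". The inputs are a standardized effect of 0.6, "using an alpha level of 0.05 and conservatively assumed a within-subject correlation of 0.5", and 24 completers from 30 enrolled with 20% dropout. Section 3.0 justifies the effect size this way: "As no precuneus rTMS pilot data was available, this standardized effect size of 0.6 is considered a conservative estimate to detect significant results". Section 13.0 gives the same reason.

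The Statistical Analyses text of section 13.0 plans more than one kind of analysis:

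- **Primary.** A mixed model for change scores, from which "we will compare the treatment difference in change score between 1 Hz and Sham as well as 20 Hz and Sham". On level and sidedness: "Statistical tests will be performed based on two-sided test at the 5% level of significance".
- **Secondary.** Two mediation analyses, each with four steps that must all be met. Step one: "a significant relation of treatment to the change in connectivity is required in (1", where (1) is the outcome model. Step two: "a significant relation of treatment to the change in activation of the precuneus is required in (3", where (3) is the mediator model. Step three needs a significant mediator term with treatment in the model. Step four needs the treatment coefficients to be smaller in absolute value once the mediator is included.

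Section 2.0 also sets a third primary aim, which "is to characterize the relationships between EM performance and changes in precuneus functional activation and connectivity". No power calculation or assumed mediator-outcome correlation is given for the mediation rule or for this association.

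**The concern.** The opening words of the power sentence reach every planned analysis, but the calculation behind it fits one type only: a single treatment difference. A rule that requires several tests to succeed together will usually have less power than one of those tests. A reader who takes the sentence at face value would credit the mediation rule with an 80% chance of success when mediation is real, and could give an unmet rule more weight than it deserves. This matters somewhat because section 1.0 presents the study as target-engagement data to inform later trials.

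The second issue is the word conservative as applied to 0.6. Lack of pilot data is a reason to be unsure of the effect size. It does not show that the chosen value is cautious.

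**Working it through.** **1. Reproducing the stated figure.** Inputs from section 13.0: n = 24, effect d = 0.6, within-subject correlation ρ = 0.5, two-sided 5%.

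- Enrolment: 30 × (1 − 0.2) = 24.
- Effect on the difference scale: dz = d / √(2(1 − ρ)) = 0.6 / √1 = 0.6.
- Noncentrality: 0.6 × √24 = 2.94.
- Error degrees of freedom: 23 for a paired t. For the three-period crossover with subject, period and treatment effects: 24 × 3 − 24 − 2 − 2 = 44.
- Power (noncentral t): **0.804** with 23 df, **0.820** with 44 df.

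The stated 0.8 is therefore right for one unadjusted contrast on one measure.

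**2. Sensitivity to the effect size.** With d = 0.5 and ρ = 0.5, the noncentrality is 0.5 × √24 = 2.45 and power is **0.650** (23 df) or **0.669** (44 df).

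**3. The mediation rule, judged per contrast.** The plan gives no mediator-outcome correlation, so r below is an assumption: the within-subject residual correlation between mediator and outcome. Crossovers were simulated with 24 subjects, six sequences and three periods. True effects were −0.6 (1 Hz) and +0.6 (20 Hz) on both mediator and outcome, and the within-subject residual variance was 0.5. Models adjusted for subject, period and treatment, with 44 error df (43 with the mediator). The rule was scored for 20 Hz versus sham.

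A hand check comes first. At r = 0, steps one and two are independent, so they pass together with probability 0.820 × 0.820 = 0.672; the simulation gives 0.67. The full rule can never exceed this joint probability, which rises only slowly with r.

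**4. The same rule with omnibus treatment tests.** Section 13.0 does not say whether a relation of treatment means one contrast or the 2-df test. With true effects of −0.6, 0 and +0.6, the noncentrality is 24 × (0.36 + 0.36) / 0.5 = 34.6, so steps one and two almost always pass and step three drives the result.

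| Assumed r | Steps 1 and 2, one contrast | Step 3 alone | Full rule, one contrast | Full rule, omnibus |
|---|---|---|---|---|
| 0.2 | 0.69 | 0.26 | 0.18 | 0.26 |
| 0.3 | 0.69 | 0.53 | 0.36 | 0.52 |
| 0.4 | 0.70 | 0.79 | 0.55 | 0.78 |
| 0.5 | 0.71 | 0.95 | 0.67 | 0.93–0.94 |
| 0.7 | 0.74 | 1.00 | 0.74 | above 0.93 |
| 0.95 | 0.79 | 1.00 | 0.79 | above 0.93 |

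The omnibus range at 0.5 depends on whether step four is required for both contrasts or for 20 Hz only.

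**5. What r means.** With equal residual variances and equal effects, the mediator coefficient is r. The indirect effect is then r × 0.6 out of a total of 0.6, so r is also the mediated share. At r = 0.2, 80% of the effect bypasses the mediator.

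**6. The correlation of 0.5.** Change scores at two visits share one baseline. If all visits have variance σ² and common correlation c, their covariance is σ²(c − c − c + 1) = σ²(1 − c) and their variance is 2σ²(1 − c). The ratio is exactly 0.5.

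**The case against.** The strongest reply is that the sentence limits itself. It speaks of detecting a treatment difference, the paragraph in section 13.0 opens with the effect of stimulation on memory performance or neurocircuitry, and the primary analysis uses the same term for its contrasts on three measures. On that reading the claim covers each measure, and 0.8 is correct. This largely stands, and it is why the point is minor. But the sentence still opens by covering all planned analyses, in two places, and the first two mediation steps are themselves tests of treatment.

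Several stronger readings are tempting, and the documents do not support them:

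- *The study is underpowered for its primary contrasts at the planned inputs.* It is not; the figure reproduces.
- *The mediation rule always falls below 0.8.* Only the per-contrast reading gives that. Under an omnibus test it passes 0.8 by r = 0.5, and section 13.0 does not settle which is meant. The lowest figures also describe cases where most of the effect is unmediated.
- *The correlation of 0.5 is optimistic.* It follows from a shared baseline under equal variances and correlations. The baseline visit may fall up to 30 days before the stimulation visits, which are 7 days apart (Attachment 1). If correlation fades with time, the value could exceed 0.5. Stimulation might alter this, so it is not proof either way.
- *The association between memory and brain measures is underpowered.* No figure is wrong there; its power could be high or low depending on an unstated correlation.
- *An unmet rule will be reported as evidence against mediation.* Section 13.0 states only what will be concluded if all four steps are met.

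**Conclusion.** A minor correction to the scope of a stated power. The 0.80 to 0.82 holds for each single active-versus-sham contrast on one measure at an unadjusted two-sided 5% level. It does not transfer to the mediation rule. Judged per contrast, that rule stays below 0.8 at every correlation examined up to 0.95. Judged by omnibus tests, it is below 0.8 up to about 0.4 and above it from 0.5. These mediation figures assume effects of 0.6 on both mediator and outcome, 24 completers and a residual correlation that the plan does not give; partial data from dropouts could add some information. Calling 0.6 conservative for want of pilot data does not follow, and a modestly smaller effect takes single-contrast power to about two-thirds.

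**What to change.** In section 3.0 (Sample Size) and section 13.0 (Power Analyses):

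- Replace the opening words of the power sentence with: *For each active-vs-sham contrast on each measure, at an unadjusted two-sided 5% level.*
- Add: *The mediation and EM-brain association analyses were not separately powered; their power depends on a mediator-outcome correlation that is not known.*
- Describe 0.6 as an assumption rather than a conservative estimate, and add: *Power is about 0.65-0.67 at effect size 0.5.*

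The within-subject correlation of 0.5 may stay as a stated assumption. Leave the mediation analyses, enrolment and the primary model unchanged.

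The cost is wording in two places. The stated power then covers fewer analyses and looks slightly less favourable.

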#### *Statistical Analyses*

[figure not shown]
Intent-to-treat (ITT) analysis will be conducted, and thus all randomized subjects will be included. ITT is the most conservative approach for detecting a treatment effect, because the inclusion of subjects who do not complete the intervention will serve to underestimate rather than overestimate any treatment effect. Sensitivity analyses including a subset analysis using a “completers only” analysis will be performed to test the robustness of the findings. Statistical tests will be performed based on two-sided test at the 5% level of significance.

Descriptive characteristics at baseline will be summarized for the whole sample. For continuous variables, the mean and standard deviation will be presented. For categorical variables, the number and percent will be reported.

Primary analyses: For each subject, change scores in activation of the precuneus (aim 1), functional connectivity (aim 2), and EM performance (aim 3) will be calculated at each treatment by using (post - baseline). We will employ a mixed model for repeated measures ANCOVA, of the general form for each measure:  $change_{ijk} = \mu + \alpha_i + b_{ij} + \gamma_k + \beta X_{ijk} + \tau_d(i, k) + e_{ijk}$ , where  $\mu$  is overall mean;  $\alpha_i$  is the effect of the  $i$ th treatment sequence ( $i = 1, 2, \dots, 6$ );  $b_{ij}$  is the random effect with variance  $\sigma_b^2$  for the  $j$ th subject ( $j = 1, 2, \dots, 24$ ) of the  $i$ th treatment sequence;  $\gamma_k$  is the period effect ( $k = 1, 2, 3$ );  $\beta X$  is the baseline value;  $\tau_d(i, k)$  is the direct effect of the treatment administered in period  $k$  of sequence group  $i$ ; and  $e_{ijk}$  is the random error with variance  $\sigma^2$  for the subject in period  $k$ . Based on this model, we will compare the treatment difference in change score between 1 Hz and Sham as well as 20 Hz and Sham. Under the assumption of missing at random, this mixed effect model will provide the unbiased estimates.

Secondary analyses: We expect two mediation relations: (1) the treatment affects the connectivity through the activation of the precuneus; and (2) the treatment affects the EM performance through the activation of the precuneus. We use the first mediation as an example. The following 3 equations proposed by Baron and Kenny will be analyzed in order to establish mediation:  $change_{ijk} = \mu + \alpha_i + b_{ij} + \gamma_k + \beta X_{ijk} + \tau_d(i, k) + e_{ijk}$  (1);  $change_{ijk} = \mu + \alpha_i + b_{ij} + \gamma_k + \beta X_{ijk} + \gamma M_{ijk} + \tau_d(i, k) + e_{ijk}$  (2); and  $M_{ijk} = \mu + \alpha_i + b_{ij} + \gamma_k + \beta X_{ijk} + \tau_d(i, k) + e_{ijk}$  (3). Four steps are to be evaluated. First, a significant relation of treatment to the change in connectivity is required in (1). Second, a significant relation of treatment to the change in activation of the precuneus is required in (3). Third, mediator, the change in the activation of the precuneus, must be significantly associated with change in connectivity when both treatment and mediator are controlled as covariates. Fourth, the coefficients of treatment in (1) must be larger (in absolute value) than the coefficients of treatments in (2). If four steps are met, we will consider that the change in activation of the precuneus is mediator of the relationship between treatment and change in connectivity.

**Brain Imaging Analyses:** **Aim 1.** Data analysis of the blood-oxygen level-dependent (BOLD) time series will utilize standard preprocessing through the AFNI software package. Standard preprocessing includes motion correction, despiking, detrending, smoothing, and exclusion of signal and motion outlier time points. Each condition's timing will be convolved with a hemodynamic response function to model an ideal response for that condition. General linear modeling will provide a regression coefficient estimate (beta) of the BOLD response to each condition (Target correct; Foil correct; Target incorrect; Foil incorrect). We will also include regressors of no interest for motion and motion derivatives to reduce noise. For our primary analysis, we will create a region of interest (ROI) as a 10-mm radius sphere around our rTMS target in the precuneus. **fMRI Contrast:** Each event type will be modeled separately. Brain activity will be examined by contrasting the estimated beta coefficients for correct trials only (Target correct vs. Foil correct). We will **extract the mean response from this contrast from our precuneus ROI** and evaluate the aim via a mixed model for repeated measures. **Aim 2.** Beyond standard preprocessing, time-series data will be filtered to extract low frequency (< 0.08 hz) BOLD data. The ANATICOR approach (within AFNI) will be used to reduce noise from physiological or hardware sources. ANATICOR utilizes tissue segmentation to control for spatially coherent fluctuations emanating from non-gray matter. Structural regions of interest (ROIs) will be defined on each side with Talairach-based atlases available via AFNI software for the ACC and bilateral middle frontal gyrus, in addition to the spherical precuneus ROI. Visual inspection of ROIs will ensure their correct position. The mean preprocessed time series will be extracted from each ROI, and time-series correlations between ROIs will be calculated. These correlations will be used as the dependent variable in a mixed model for repeated measures ANCOVA, with post-hoc tests as necessary. Supplementary analyses will examine connectivity differences of the precuneus ROI across the entire brain (corrected  $p < .05$ ).

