### *Discontinuation*

Subjects will be discontinued under the following circumstances:

1. During the course of the study, subjects with an interruption of stimulation administration
2. Subjects unwilling or unable to complete study assessments or procedures
3. Subjects who experience seizure occurrence at any point during study participation
4. Subjects who require a change in dose of antipsychotic medication or the addition of a new antipsychotic medication

5. Subjects experiencing an exacerbation of illness requiring an increased level of care or one judged to be clinically significant by the PI.

If subjects discontinue from the study, completion of discontinuation assessments will be at the discretion of the PI. A subject may withdrawn from the study at any time at his/her own request, or may be withdrawn at any time at the discretion of the PI for safety, behavioral, or administrative reasons.

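### Completers-only, the one named robustness check, is weak and cannot detect dropout that is missing not at random

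*Combined protocol and SAP*

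**What the plan says.** All of this stands in section 13.0 unless noted.

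- Analysis set (Statistical Analyses): "Intent-to-treat (ITT) analysis will be conducted, and thus all randomized subjects will be included". The section adds that this is conservative, because non-completers pull the estimated effect down rather than up.
- Missing data: "Under the assumption of missing at random, this mixed effect model will provide the unbiased estimates". No imputation is described, so the model uses whatever post-session scans exist.
- Robustness: "Sensitivity analyses including a subset analysis using a “completers only” analysis will be performed to test the robustness of the findings". The wording leaves the list open, but nothing else is named, and no analysis under missing not at random (MNAR) appears anywhere.
- Size (Power Analyses): "We plan to enroll 30 subjects and anticipate a 20% drop out rate, thus yielding 24 completers".
- Section 11.0, Discontinuation, lists reasons for leaving that could be related to outcome, for example: "Subjects experiencing an exacerbation of illness requiring an increased level of care or one judged to be clinically significant by the PI". Assessments after discontinuation are left to the investigator's discretion.
- The model formula indexes subjects j = 1 to 24 within sequence i = 1 to 6.

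**The concern.** The primary estimates depend on missing at random. A useful sensitivity analysis would relax that assumption. Completers-only tightens it: it discards the partial data of subjects who leave, and is in general valid only under a stronger condition. In a three-period crossover the two analyses are also nearly the same. A subject who leaves before any post-session scan adds nothing to either, and a subject with one scan adds little to a within-subject contrast.

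At stake is the report's claim of robustness. If dropout is related to the unseen response, the two results may agree closely while both are wrong. The study is meant to supply preliminary target-engagement data for later trials, so an untested effect size could be carried forward.

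**Working it through.** **1. The plan's own figure.** Inputs from Power Analyses: n = 24, effect 0.6, correlation 0.5, alpha 0.05; two-sided from Statistical Analyses. Standardized paired effect = 0.6/√(2(1 − 0.5)) = 0.60. Noncentrality = 0.60 × √24 = 2.94, df = 23, power 0.804. Enrolment: 24/(1 − 0.2) = 30. Both stated figures reproduce.

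**2. Shared data.** 24 completers × 3 sessions = 72 post-session scans. Six dropouts can add at most 6 × 2 = 12. The shared fraction runs from 72/84 = 86% to 72/72 = 100%.

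**3. How close the two estimates are.** Assumptions: 30 subjects, five per sequence, one dropout per sequence, correlation 0.5, variances known, fixed effects for sequence, period and treatment. For completers, Var = 2(1 − 0.5)/24 = 0.0417, SE 0.204. The all-data generalized least squares estimate is efficient, so correlation = √(Var_all/Var_completers) and SD of the difference = √(Var_completers − Var_all).

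| Sessions before dropout | SE, all data | Added information | Correlation | SD of difference |
|---|---|---|---|---|
| none | 0.204 | 0% | 1.00 | 0 |
| one | 0.201 | 4% | 0.98 | 0.04 |
| two | 0.191 | 14% | 0.94 | 0.07 |

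Simulation gave 0.93 to 0.94 for the last row, and 0.97 for a mix of two dropouts of each kind.

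**4. Behaviour under different dropout mechanisms.** 2,000 simulated trials each, true 20 Hz effect 0.60, about 20% dropout, the plan's fixed effects, known variances. The mechanisms are assumptions; the documents give none.

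| Dropout | All data | Completers | Correlation | Mean absolute difference |
|---|---|---|---|---|
| completely at random | 0.592 | 0.592 | 0.97 | 0.036 |
| at random, driven by the previous outcome | 0.607 | 0.592 | 0.95 | 0.050 |
| MNAR: poor 20 Hz outcomes lost | 0.760 | 0.737 | 0.98 | 0.033 |
| MNAR: poor outcomes lost in any condition | 0.576 | 0.578 | 0.97 | 0.038 |

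In the third row both analyses overstate the effect, by 0.16 and 0.14, and differ on average by about 0.02. In the second row, where missing at random holds, they also differ on average by about 0.02. Against an SE of about 0.20, one trial could not tell these cases apart. The third row also shows that including non-completers need not lower the estimate: there it is the higher of the two. The fourth row shows that MNAR dropout need not bias the contrast much.

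**5. What a delta adjustment would show.** Assume all six dropouts lack the contrast, 24 completers have mean difference 0.6 and SD 1, and the six have mean m and SD 1.

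- Estimate = (24 × 0.6 + 6m)/30.
- Sum of squares = 23 + 5 + (24 × 6/30)(0.6 − m)²; SE = √(SS/29/30).
- For multiple imputation, add (6/30)² × (1/24 + 1/6) = 0.0083 to SE², with about 22 df.

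| Dropouts' effect m | Estimate in 30 | SE (single) | p, single imputation | p, multiple imputation |
|---|---|---|---|---|
| 0 | 0.48 | 0.185 | 0.015 | about 0.03 |
| −0.3 | 0.42 | 0.191 | 0.036 | about 0.06 |
| −0.6 | 0.36 | 0.200 | 0.083 | about 0.12 |

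Completers-only returns 0.60 with t = 0.6 × √24 = 2.94 and p = 0.007 in every row.

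**The case against.** - **Purpose.** The plan promises a test of robustness, not a test of missing at random, and no analysis of observed data can test that assumption. This stands. A tipping-point analysis does not test it either; it shows how large a departure would change the conclusion, which completers-only does not.
- **The comparison is not empty.** The two estimates separate on average when dropout depends on observed outcomes (0.607 against 0.592), and the SD of their difference can reach about 0.07 against an SE of 0.19. This stands. A reader might infer that agreement shows nothing at all about robustness; that goes too far. The check is weak, and it cannot detect MNAR dropout.
- **The index.** A reader might infer from j = 1 to 24 that the primary analysis is itself confined to the 24 expected completers. The documents do not support this. The index runs within each sequence, so read literally it gives 6 × 24 = 144 subjects, and the same section includes all randomized subjects. It is a notation slip.
- **Open list.** Other sensitivity analyses may be added. It would be wrong to say that informative dropout will never be examined; none is pre-specified to examine it.
- **Proportion.** This is a single-site pilot with about six expected dropouts. In the illustration significance is lost only if the dropouts' effect is reversed, and nothing in the documents suggests such a reversal. This stands, and it limits the weight of the point.

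**Conclusion.** The point holds as a minor one. Completers-only needs a stronger missingness assumption than the primary model, shares 86% to 100% of its scans at the planned dropout, and gives estimates that correlate with the primary at about 0.93 to 1.00. It cannot reveal MNAR dropout: under one assumed mechanism both analyses were biased upward by about 0.14 to 0.16 and still agreed. The section's statement that including non-completers understates the effect is not assured for an available-data mixed model without imputation.

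The overlap bound rests only on the plan's figures. The correlations also assume the plan's correlation of 0.5 and particular dropout times. The biases and the illustrative p-values rest on assumed mechanisms and dropout effects, and the illustration is an upper bound because it treats all six contrasts as missing. None of this shows that the trial's result will be biased.

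**What to change.** 1. Pre-specify a delta-adjusted (tipping-point) sensitivity analysis of the 1 Hz–sham and 20 Hz–sham contrasts for the outcomes listed under Primary analyses. Impute missing post-session values under the primary model by multiple imputation. Shift the missing active-condition values towards and past no effect, state the shift used for missing sham values (for example zero), and report the shift at which the conclusion changes.
2. Keep completers-only, labelled as descriptive.
3. Remove or qualify the statement that including non-completers can only understate the effect.
4. As a notation correction only, replace j = 1 to 24 with j = 1 to n_i in sequence i, with the n_i summing to the 30 planned subjects.

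The cost is SAP wording and a few hours of programming, with no new data. The reported conclusion may look less firm.
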